9.5.3 Analysis of Efficacy Variables

All efficacy analyses will be conducted on both the ITD and PP populations. The ITD population will be the primary analysis set.

9.5.3.1 Primary Endpoints Arms 1- 2

Precision endpoints will be assessed estimating the mean, standard deviation, n, minimum, median, and maximum of the signed differences, calculated as change from the initial measurement. The RMSD will be calculated and a 95% confidence interval on its value will be provided.

Stability of the mean/variance relationship will be assessed by the coefficient of variation of the differences for active RA subjects and HC subjects at 60 minutes and 180 minutes. 95% confidence intervals for the difference in CVs following the methods of ([Forkman 2009](#)) and from the bootstrap sampling distribution of the difference of the CVs will be provided based on N = 5000 bootstrap samples.

9.5.3.2 Secondary Endpoints Arms 1- 2

The normal ranges of ΔTUV_{joint} will be estimated from data collected from HC subjects (Arm 1 only) at 60 minutes and 180 minutes post-injection. The mean, standard deviation, n (number of joints), and quantile regression estimates of the 5 and 95 percentiles will be provided for shoulder, elbow, wrist, MCP, PIP, and knee.

9.5.3.3 Primary endpoint Arm 3

The Kendall rank correlation between $\Delta TUV_{global[5w]}$ with $\Delta CDAI_{12w}$ and $\Delta CDAI_{24w}$ will be computed and a 95% confidence interval for its value will be computed using Fisher's Z-transformation. Similarly, the Kendall rank correlation between $\Delta TUV_{global[5w]}$ with ΔACR_{12w} and ΔACR_{24w} (overall scores only) will be computed and a 95% confidence interval for its value will be computed using Fisher's Z-transformation.

9.5.3.4 Secondary endpoint Arm 3

The Kendall rank correlations between $\Delta TUV_{global[5w]}$ with the subscores of ΔACR_{12w} and ΔACR_{24w} (including tender joint count, swollen joint count, Patient assessment of global disease activity, Rheumatologist assessment of global disease activity, Patient assessment of pain, Patient assessment of physical function, Acute-phase reactant value) will be computed and a 95% confidence interval for its value will be computed using Fisher's Z-transformation.

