6.0 OTHER RELEVANT DATA ANALYSES/SUMMARIES	29
6.1 Patient Completion	29
6.3 Study Drug Administration.....	29
6.4 RA Evaluation and Screening Physical Exam.....	29
6.5 Concomitant Medications.....	29
7.0 LIST OF ANALYSIS TABLES, FIGURES AND LISTINGS	31
9.0 REFERENCES.....	35
APPENDIX A – TABLES, FIGURES AND LISTING SPECIFICATIONS	36
APPENDIX B – TABLE SHELLS	38

INTRODUCTION

Description

This Statistical Analysis Plan (SAP) is consistent with Amendment 4 of the study protocol (dated 2 February 2021) and includes the latest details of efficacy and safety summaries to be included in the clinical study report (CSR).

The preparation of this SAP was done in accordance with STATKING Clinical Services SOP SCI 02-54, Statistical Analysis Plans.

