2.2 Analysis Populations

The following analysis populations will be used in the study:

Safety Population – The safety population includes all patients that have been enrolled in the study and injected with at least one dose of Tc 99m tilmanocept.

Intent-to-Diagnose (ITD) Population – The ITD population includes all patients that have been enrolled in the study, injected with Tc 99m tilmanocept, and received all imaging and evaluations necessary for the primary endpoint(s) appropriate to their respective arm.

Per Protocol (PP) Population: The PP population will include all ITD subjects without major protocol violations. All protocol deviations will be classified as major or minor prior to database lock.

All efficacy analyses will be carried out on the ITD and PP populations with the ITD population being the primary analysis set. All analyses of safety data and baseline subject characteristics will be carried out on the safety population. A data listing displaying the patients excluded from each population will be created, as shown in Appendix B.

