4.1.1 Primary efficacy variables

The primary efficacy variables for this study are:

- Quantitative measurement of TUV_{joint} (all arms) and TUV_{global} (Arms 2 and 3 only)
- CDAI scores at baseline, 12 (± 1) weeks and 24 (± 1) weeks (Arm 3 only)
- DAS28 scores at baseline, 12 (± 1) weeks and 24 (± 1) weeks (Arm 3 only)
- ACR Response Criteria at 12 (± 1) weeks and 24 (± 1) weeks (Arm 3 only).

The primary efficacy variables of this study in Arms 1 and 2 are:

- The camera-specific precision of TUV_{joint} and TUV_{global} in subjects with active RA and healthy controls, which is defined as the Root Mean Square Difference (RMSD) between the consecutive 15-minute planar images.
- The stability of the mean/variance relationship, which is assessed by comparing the Coefficient of Variation (CV) of TUV_{joint} and TUV_{global} in subjects with active RA and healthy controls.

An added primary variable in Arm 2 only is:

- The longitudinal (8-day) precision of TUV_{joint} and TUV_{global} in subjects with active RA, which is defined as the RMSD of the TUV between the baseline and 8 day image at the same time point.

The primary endpoints in Arm 3 are:

- The Kendall rank correlation of $\Delta TUV_{global[5w]}$ with the response to new anti-TNF α bDMARD therapy defined as $\Delta CDAI_{12w}$ and $\Delta CDAI_{24w}$ (overall scores only) in study arm 3.
- The Kendall rank correlation of $\Delta TUV_{global[5w]}$ with the response to new anti-TNF α bDMARD therapy defined as the changes from baseline in DAS28 and in each of the ACR Response Criteria components at 12 (± 1) weeks and at 24 (± 1) weeks in study arm 3.

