4.1.2 Secondary efficacy variables

- Qualitative evaluations of SPECT/CT image detecting localization of Tc 99m tilmanocept in the synovial spaces of the bilateral hands and wrists. (Arm 2 only).
- CDAI score at baseline (CDAI_{0w}), 12 (CDAI_{12w}) and 24 weeks (CDAI_{24w}) (Arm 3 only).
- ACR Response Criteria at 12 and 24 weeks (Arm 3 only).
- Constituent scores of the ACR Response Criteria at baseline, 12 weeks, and 24 weeks, including:
 - TJC
 - SJC
 - Patient assessment of global disease activity
 - Rheumatologist assessment of global disease activity
 - Patient assessment of pain
 - Patient assessment of physical function
 - Acute-phase reactant value.
- Constituent scores of the CDAI score
 - TJC
 - SJC
 - Patient Global Assessment
 - Physician Global Assessment.

The secondary efficacy endpoints for this study are:

ARMS 1-2

- The temporal stability of TUV_{joint} and TUV_{global} using a 150 mcg tilmanocept mass dose/10 mCi radiolabeling dose, which is defined as the squared difference between the 1-hour and 3-hour planar images. (This endpoint was analyzed to the sponsor's satisfaction in IA-3.)

ARM 1

- The normal upper limit of TUV_{joint} in HC subjects, which is defined the upper limit of a 95% prediction interval at 60 ±15 minutes:
 - TUV_{joint} of evaluated joints (i.e., wrists, MCPs, PIPs, knees, elbows, shoulders in Arms 1 and 2, and wrists, MCPs, and PIPs in Arm 3).

ARM 2

- The qualitative evaluations of SPECT/CT in detecting localization within synovial spaces of the bilateral hands and wrists.

ARM 3

- $\text{TUV}_{\text{global}[0w]}$ and response to new anti-TNF α bDMARD therapy defined by the change from baseline (CFB) of CDAI to 12 ± 1 weeks and 24 ± 1 weeks (ΔCDAI_{12w} and ΔCDAI_{24w} , respectively) and by the changes from baseline in each of the ACR Response Criteria components at 12 (± 1) weeks and at 24 (± 1) weeks.
- $\Delta\text{TUV}_{\text{global}[5w]}$ and response to new anti-TNF α bDMARD therapy defined by the CFB of CDAI to 12 ± 1 weeks and 24 ± 1 weeks (ΔCDAI_{12w} and ΔCDAI_{24w} , respectively).
- $\Delta\text{TUV}_{\text{global}[12w]}$ and $\Delta\text{TUV}_{\text{global}[24w]}$.

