4.2 Analysis of Efficacy Variables

4.2.1 Primary Efficacy Variables

Primary Endpoints for Arms 1 and 2

All TUV data will be analyzed with summary statistics (mean, standard deviation, n, minimum, median, maximum) by study arm and joint.

Precision endpoints will be assessed estimating the mean, standard deviation, n, minimum, median, and maximum of the signed differences (CFB). The RMSD will be calculated

$$RMSD = \frac{1}{n-1} \sum_{k=1}^n (y_k - w_k)^2$$

where y_k and w_k are the measurements at the two timepoints and k represents the subject number. A 95% confidence interval for the RMSD based on Normal theory will be provided, as will a 95% bootstrap confidence interval based on $N = 5000$ bootstrap samples. Timepoints analyzed in this way will include the 60 minute A and B scans, the 180 minute A and B scans, and the difference between the 60 and 180 minute A scans. These will be done for all joints assessed and for TUV_{global} . (These analyses were completed to the sponsor's satisfaction in IA-3.)

Primary Endpoint for Arm 2 Only

The longitudinal (8-day) variation of TUV will be analyzed for each DAS28 joint and globally. The signed differences will be analyzed with descriptive statistics and the RMSD will be calculated as defined for Arm 2 above. A 95% confidence interval for the RMSD based on Normal theory will be provided, as will a 95% bootstrap confidence interval based on $N = 5000$ bootstrap samples will be computed, and 95% confidence limits for its value will be provided. This will be done for TUV_{joint} for all evaluated joints and TUV_{global} in the 60 minute images using the "A" image at baseline. The fraction of unsigned ΔTUV_{global} values less than 7.5% will be summarized in a frequency table and an exact binomial test of the hypotheses described in Section 1.3 will be included for each timepoint.

Primary Endpoints for Arm 3 Only

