4.2.2 Secondary Efficacy Variables

Secondary Endpoints for Arm 1 only

The normal ranges of TUV_{joint} will be estimated from data collected from healthy subjects (study arm 1) at 60 minutes post-injection. The mean, standard deviation, n (number of joints), and quantile regression estimates of the 5 and 95 percentiles will be provided for shoulder, elbow, wrist, MCP, PIP, and knee. All joints will be summarized individually.

Secondary Endpoints for Arms 1 and 2

The temporal quantitative stability of the images will be assessed by computing the fraction of observations for which $|\Delta TUV_{global}| \leq 0.075$ for the difference between the 60 and 180 minute images. The hypotheses

$$H_0: \pi \leq 0.80$$

vs

$$H_a: \pi > 0.80,$$

where π represent the fraction of unsigned differences less than 7.5% will be tested with an exact test and a Clopper-Pearson (exact) 95% confidence interval for p will be provided. The RMSD will be analyzed by joint, providing 95% confidence intervals for the RMSD using both Normal theory methods and a bootstrap estimate with 5000 bootstrap replications.

The 80th and 90th percentiles of the distribution of unsigned differences will be estimated using quantal regression methods. (These analyses were completed to the sponsor's satisfaction in IA-3.)

Secondary Endpoint for Arm 2 only

Qualitative evaluations of SPECT/CT imaging in localizing tilmanocept uptake will be estimated from the active RA subjects (Arm 2 only) on the joints of the hands and wrists. A frequency table of counts and percent of subjects will be provided.

Secondary Endpoints for Arm 3 only

All RA quantitative assessment variables (CDAI, ACR Response Criteria component scores, DAS28 score, and HAQ-DI) will be summarized by arm, computing the mean, standard deviation, number of observations, minimum, median, and maximum for the observed values at each time point and for the change from baseline for values collected after Day 0. The ACR Response Criteria will be summarized with a frequency table of the highest ACR Response level (None, ACR20, ACR50, ACR70) attained by that subject at that time point. That is, a subject who satisfies ACR50 also satisfies ACR20 but will not appear in the frequency count for ACR20.

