7.0 List of Analysis Tables, Figures and Listings

Table No.	Table Title	Included in Final Tables	Shown in Appendix B
1	Subject Disposition by Study Arm	X	X
2	Demographics and Baseline Data Summary Statistics by Arm - Continuous Variables (Safety Population)	X	X
3	Demographics and Baseline Data Summary Statistics by Arm – Categorical Variables (Safety Population)	X	X
4	Summary of Study Drug Administration by Arm (Safety Population)	X	X
5	Summary of TUV by Arm, Study Day, and DAS28 Joint (ITD population)	X	X
6	Summary of TUV by Arm, Study Day, and DAS28 Joint (PP Population)	X	
7	Summary for Eight-Day Longitudinal Stability of TUV (Arm 2 Only) (ITD Population)	X	X
8	Summary for Eight-Day Longitudinal Stability of TUV (Arm 2 Only) (PP Population)	X	
9	Analysis of Eight-Day Longitudinal Stability of Δ TUV _{global} (ITD population)	X	X
10	Analysis of Eight-Day Longitudinal Stability of Δ TUV _{global} (PP population)	X	X
11	Summary for Day 0 vs Day 8 RA Images (ITD Population)	X	X
12	Summary for Day 0 vs Day 8 RA Images (PP Population)	X	
13	Assessment of Mean/Variance Relationship by Time Point (ITD Population)	X	X
14	Assessment of Mean/Variance Relationship by Time Point (PP Population)	X	
15	Normal Range of TUV in Healthy Control Subjects (ITD Population)	X	X
16	Normal Range of TUV in Healthy Control Subjects (PP Population)	X	
17	RA Status Summaries (ITD Population)	X	X
18	RA Status Summaries (PP Population)	X	
19	Kendall Rank Correlation of Δ TUV, Δ CDAI, Δ ACR Response Criteria Components, and Δ DAS28 with Δ TUV at 5 weeks in Arm 3 (ITD Population)	X	X
20	Kendall Rank Correlation of Δ TUV, Δ CDAI, Δ ACR Response Criteria Components, and Δ DAS28 with Δ TUV at 5 weeks in Arm 3 (PP Population)	X	
21	Kendall Rank Correlation of Δ TUV, Δ CDAI, Δ ACR Response Criteria Components, and Δ DAS28 with Δ TUV at 12 weeks in Arm 3 (ITD Population)	X	X
22	Kendall Rank Correlation of Δ TUV, Δ CDAI, Δ ACR Response Criteria Components, and Δ DAS28 with Δ TUV at 12 weeks in Arm 3 (PP Population)	X	

Table No.	Table Title	Included in Final Tables	Shown in Appendix B
23	Kendall Rank Correlation of Δ CDAI, Δ ACR Response Criteria Components, and Δ DAS28 with Δ TUV at 24 weeks in Arm 3 (ITD Population)	X	X
24	Kendall Rank Correlation of Δ CDAI, Δ ACR Response Criteria Components, and Δ DAS28 with Δ TUV at 24 weeks in Arm 3 (PP Population)	X	
25	Frequency Counts of Localization in SPECT/CT Imaging in RA-2 Subjects (ITD Population)	X	X

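### The primary repeat-scan RMSD and the 60 versus 180 minute analyses are closed at Interim Analysis 3 with no final table, and that analysis's TUV formula and Arm 1-2 counts are not stated; separately, ACPA is cut at both 85 and 70

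*SAP*

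**What the plan says.** SAP 4.1.1 lists, as a primary variable for Arms 1 and 2, camera-specific precision, defined as the "Root Mean Square Difference (RMSD) between the consecutive 15-minute planar images". SAP 4.2.1 sets out the calculation for three pairs: the two 60 minute scans (A and B), the two 180 minute scans, and the 60 versus 180 minute A scans. The paragraph is written in the future tense but ends "These analyses were completed to the sponsor's satisfaction in IA-3". SAP 4.1.2 says of temporal stability "This endpoint was analyzed to the sponsor's satisfaction in IA-3", and SAP 4.2.2 repeats the remark after the exact test and percentiles for 60 versus 180 minutes.

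SAP 2.2 states: "All efficacy analyses will be carried out on the ITD and PP populations with the ITD population being the primary analysis set". Protocol 9.5.3 agrees: "All efficacy analyses will be conducted on both the ITD and PP populations".

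On ACPA, algorithms 3, 6 and 7 in SAP 4.2.2 predict success above 85 and failure at 85 or below. The same section then describes a summary table with categories split at 70. The Table 66 shell also uses 70, and its footnote says the categories are the levels used in the algorithms.

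**The concern.** An endpoint named as primary should be reported from the final data, on the defined populations, with the final version of the measurement. Here it is treated as finished at an interim analysis whose stated purposes (SAP 2.4) were to estimate treatment effects on TUV and to optimize the metric. The criterion given for closing it is the sponsor's satisfaction, not a data cut or a population.

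Two things are at stake. The clinical study report may contain no ITD or PP result for a primary endpoint, or may carry one from an unstated sample. And because the metric was still being developed, that result may describe a different quantity: an RMSD of a ratio to a brain region, multiplied by 100, cannot be compared with an RMSD of a ratio to the hand.

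The sizing of Arm 1 is also affected. SAP 1.3 and Protocol 9.4 base its 38 subjects on temporal stability, and the Protocol synopsis bases them on precision in healthy controls. Both analyses are among those treated as closed.

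**Working it through.** **1. Is there a final table?** The list in SAP 7.0 and the shells in Appendix B were read against the three closed comparisons.

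| Tables | Content | Covers A/B scans or 60 vs 180 min? |
|---|---|---|
| 5, 6 | TUV by arm, study day, joint | No; no scan or post-injection time column |
| 7, 8 | Eight-day stability, Arm 2, including RMSD | No |
| 9, 10 | Eight-day exact test on global TUV | No |
| 11, 12 | Day 0 versus Day 8 | No |
| 13, 14 | CV comparison, HC versus RA | No |
| 15, 16 | Normal ranges in HC | No |

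The remaining tables cover disposition, baseline, dosing, Arm 3, SPECT/CT and safety. RMSD appears only in Tables 7 and 8. The other primary endpoint shared by Arms 1 and 2, the CV comparison, keeps its ITD and PP tables.

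**2. Which metric did Interim Analysis 3 use?**
- Protocol 1.1: joint intensity over a cerebral vascular region, times 100.
- SAP 1.2: joint and brain uptake were read for Interim Analysis 2.
- SAP 2.5: joint over hand. The RMSD plan follows directly, with a remark about joint pooling in Interim Analysis 3.
- SAP 4.1: joint over a reference region that is not named. The SAP abbreviation list still carries a brain reference term.

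SAP 1.2 and 2.5 together suggest that Interim Analysis 3 used the hand. No passage says so.

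**3. How many Arm 1 and Arm 2 subjects?** SAP 2.4 gives only the Arm 3 trigger: 15 through Visit 4. Interim Analysis 2 had 30 subjects from Arms 1 and 2, at least 15 of them RA. If the interims ran in order, Arm 2 had at least 15 at Interim Analysis 3. Arm 1 has no stated floor. The planned final number is 38 per arm.

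**4. What would a partial sample cost in precision?** Assume Normal differences with mean zero and the SAP 2.5 formula, RMSD = sqrt(SS/(n−1)), with SS/σ² following chi-square on n degrees of freedom. The 95% limits are RMSD × sqrt((n−1)/χ²) at the 0.975 and 0.025 quantiles.

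| n | χ² 0.975 | χ² 0.025 | Limits as multiples of RMSD | Width |
|---|---|---|---|---|
| 10 (illustration, Arm 1) | 20.483 | 3.247 | 0.66 to 1.66 | 1.00 |
| 15 | 27.488 | 6.262 | 0.71 to 1.50 | 0.78 |
| 38 | 56.896 | 22.878 | 0.81 to 1.27 | 0.47 |

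Unrounded, the width at n = 15 is 0.782/0.465 = 1.68 times that at n = 38. At n = 10 it is 1.002/0.465 = 2.15 times.

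**5. The 60 versus 180 minute exact test.** It uses the hypotheses of SAP 1.3 (fraction within 7.5% above 0.80), for which the plan states N = 38 and power 0.80 in Arm 2. That figure cannot be confirmed, because neither alpha nor the alternative is given. At one-sided 0.05, rejection needs 35 of 38, and power is 80% at a true fraction of 0.939. At one-sided 0.025 it needs 36 of 38, and the fraction is 0.959. As an illustration at one-sided 0.05 and an assumed fraction of 0.95, power is 0.88 with 38 subjects and 0.46 with 15. With 15, all 15 must succeed, since 0.80^15 = 0.035. At one-sided 0.025, rejection is impossible with 15.

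**6. ACPA.** A subject above 70 and up to 85 falls in the upper category of Table 66 but is a predicted non-responder under algorithm 7, and under algorithms 3 and 6 wherever they refer to ACPA. All three algorithms use 85, so PPV, NPV and accuracy do not depend on the 70.

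**The case against.** The endpoint has not clearly been dropped. SAP 2.5 commits to the same RMSD analyses and intervals without any completion remark, and nothing bars interim output from being carried into the study report. That stands: the fault is a conflict between 2.5 on one side and 4.2.1 with 7.0 on the other. But a list of final tables that omits a primary endpoint does not resolve the conflict in favour of reporting it.

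The metric may well have been the final one. The cerebral formula sits in the Protocol background, the Protocol defers TUV details to the SAP, and the brain read is tied only to Interim Analysis 2. That also stands as the likelier reading, and it is why a different metric is put only as a possibility. An approved plan for Interim Analysis 3 exists and may settle the matter, but the SAP does not summarise it.

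A reader might go further and infer that clinical response was used, without disclosure, to tune the metric or the cut-offs at Interim Analysis 3. The documents do not support this. Optimization on data from all three arms was planned in Protocol 9.5.6 and disclosed in SAP 2.4. The formula in SAP 2.5 shows no response-tuned parameter, and no passage links the cut-offs to the interim. The SAP is simply silent on whether response was used, so no bias in the Arm 3 results is claimed.

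**Conclusion.** The point holds, as something that should be corrected. A primary precision endpoint and the 60 versus 180 minute analyses are closed at an interim look and missing from the final table list. This conflicts with SAP 2.5 and with the ITD and PP rule in both documents. That part rests on reading alone, and confidence is high.

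The size depends on facts not given. If Interim Analysis 3 used the SAP 2.5 metric and all evaluable subjects, the effect is on reporting only. If it used 15 in an arm, the RMSD limits are about 1.7 times wider than at 38, under Normal differences with zero mean. Fifteen is an inferred floor for Arm 2 only; Arm 1 could have been smaller. If it used another reference region, the result is a different quantity. No direction of bias is claimed.

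The ACPA conflict is a plain inconsistency of small consequence: under the algorithms as written it alters one descriptive table.

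**What to change.** 1. Delete the three remarks in SAP 4.1.2, 4.2.1 and 4.2.2. Add to SAP 7.0 final tables, by reader, for 60 minute A/B RMSD, 180 minute A/B RMSD and 60 versus 180 minutes, using the SAP 2.5 metric and all evaluable Arm 1 and 2 subjects. That is 3 comparisons × 2 populations = 6 tables on the Table 7 shell with an arm column. The exact test in 4.2.2 needs a p-value, which that shell lacks, so add a Table 9 type shell for ITD and PP: 2 more tables. If Interim Analysis 3 already used this metric and all subjects, say so, give n per arm, and reproduce its results in these tables.
2. Reconcile the ACPA cut-off across algorithms 3, 6 and 7, the summary text in 4.2.2, and Table 66 with its footnote.
3. At most, add one sentence to SAP 2.4 stating which data were used to optimize the metric at Interim Analysis 3, and whether they included clinical response.

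All of this uses existing data. The tables are long: for 22 joints, 22 × 2 views × 3 readers × 2 arms + 3 global rows for Arm 2 = 267 rows in each of the four parts of the Table 7 shell. The real cost is that any difference from the interim values must be reported and explained.
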